8.2.1.2.2 Grade 3 Adverse Event

Subjects who develop a Grade 3 AE should be managed as follows:

- If the Investigator has compelling evidence that the Grade 3 AE has not been caused by investigational product, then dosing may continue after discussion with the Medical Monitor.
- Subjects who develop a Grade 3 AE that the Investigator considers related to investigational product should have the investigational product discontinued. Subjects experiencing Grade 3 AEs requiring permanent discontinuation of investigational product should be followed weekly until resolution or stability of the AE and encouraged to have withdrawal study evaluations completed.

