8.3.2 Follow-Up of Adverse Events

After the initial AE/SAE report, the Investigator is required to proactively follow each subject at subsequent visits/contacts. All SAEs and nonserious AEs will be followed until resolution, until the condition stabilizes, until the event is otherwise explained, or until the subject is lost to follow-up.

The Investigator will assess the outcome of each AE using the following criteria:

- **Recovered/Resolved:** The event has improved or subject recuperated.
- **Recovered/Resolved with sequelae:** The subject has recuperated but retained pathological conditions resulting from the prior disease or injury.
- **Recovering/Resolving:** The event is improving.
- **Not recovered/Not resolved:** The event has not improved or subject recuperated.
- **Unknown:** The outcome of the event is not known, not observed, not recorded, or refused.
- **Fatal:** Termination of life as an outcome of the AE.

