13.2 Adverse Events

All AE summaries will be restricted to TEAEs. For rollover subjects, all AEs reported in this study will be considered as TEAEs except for those AEs resolved prior to the Visit 1 date in this study. For direct-enrolling subjects, all AEs that start after the first dose of study drug will be

considered a TEAE. Verbatim terms in the eCRFs will be mapped to PTs and SOCs using MedDRA, Version 24.0.

Imputation of start and end dates of AEs

To calculate duration of AEs, the following rules will be used where applicable to impute partial or completely missing start dates or end dates:

- If only the day is missing for a start date, the 1st of the month will be imputed. If the new estimated date falls before the Visit 1 date, while the known month and year match the month and year of the Visit 1 date, the date of Visit 1 will be used as the new estimated date.
- If only the day is missing for an end date, the last day of the month will be imputed. If the new estimated date falls after the date of last study visit, the date of last study visit will be used as the new estimated date.
- If both the day and the month are missing for a start date or end date, no imputation will be used, and the duration will not be calculated.
- If the start date or end date is completely missing, duration will not be calculated.

For AEs ongoing at the end of the previous studies, duration will be computed using the DMVT-505-3103 Visit 1 date as the AE start date.

Imputation of missing relationship and/or missing severity

If relationship to treatment is missing, the event will be conservatively treated as related to study drug.

If severity is missing and the AE is reported as serious and fatal, severity will be imputed as CTCAE=5. If severity is missing and the AE is reported as serious and not fatal, severity will be imputed as CTCAE=4. If severity is missing and the AE is not reported as serious, severity will be imputed as CTCAE=3.

All TEAEs will be listed by subject, detailing the verbatim term given by the investigator, PT, SOC, onset date, end date, ongoing at the end of parent studies (Y/N), duration (days), CTCAE grade, outcome, relationship to study drug, action taken with study drug, other action taken to treat the event, AE of special interest (AESI) (Y/N), seriousness and criteria for seriousness.

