- Figures will be in black and white but can be in color to add value to the clarity and readability of a figure. Lines must be wide enough to see the line after being copied.
- The last footnotes will be
 - “Source: xxx”, where xxx indicates the source listing number(s) and/or source dataset(s) (e.g., ADaM).
 - “PROGRAM SOURCE: ...\\xx.sas, DATA CUT-OFF DATE: DDMMYY YYYY, RUN DATE: DDMMYY hh:mm”.

Listings

[figure not shown]
- If not otherwise specified, all data listings will be sorted by sequence/treatment (pivotal/PK/direct enrolling), center, subject number, visit, and date/time, as appropriate.
- All date values will be presented in a SAS date (e.g., 29AUG2001) format.
- All observed time values will be presented using a 24-hour clock HH:MM:SS format (e.g., 01:35:45 or 11:26). Seconds will only be reported if they were measured as part of the study.
- The last footnote will be
 - “PROGRAM SOURCE: ...\\xx.sas, DATA CUT-OFF DATE: DDMMYY YYYY, RUN DATE: DDMMYY hh:mm”.

Standard Calculations

Variables requiring calculation will be derived using the following formulas:

- **Days** – A duration expressed in days between 1 date (date1) and another later date (date2) is calculated using the formulas noted below:
duration in days = date2 – date1 + 1
- **Months** – A duration expressed in months is calculated using the INTCK function of SAS as follows: months=intck('month','date1'd,date2'd, 'continuous').
- **Years** – A duration expressed in years between one date (date1) and another later date (date2) is calculated as follows:
duration in years = intck('year', 'date1'd, 'date2'd, 'continuous').
- **Age** – Age at time of informed consent will be reported on the CRF.
- **Height** – Height entries made in inches (in) are converted to centimeters (cm) using the following formula:
height (cm) = height (in) × 2.54.
- **Weight** – Weight entries made in pounds (lb) are converted to kilograms (kg) using the following formula:
weight (kg) = weight (lb)/2.2046.

- **Temperature** – Temperature entries in degrees Fahrenheit are converted to degrees centigrade using the following formula:
$$\text{temp (degrees centigrade)} = 5/9 \times [\text{temp (degrees Fahrenheit)} - 32].$$
- **Body Mass Index (BMI)** – BMI is calculated using height (cm) and weight (kg) using the following formula:
$$\text{BMI (kg/m}^2\text{)} = \text{weight (kg)}/[\text{height (cm)}/100]^2\text{].}$$
- **Change from baseline** – Change from baseline will be calculated as:

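### SAP 13.2 resets a day-missing AE end date to the last study visit even when the recorded end month is later, which contradicts the recorded month and shortens the duration

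*SAP*

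**What the plan says.** SAP 13.2 gives rules for partial AE dates, introduced as a means of calculating duration.

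- **End date, day missing.** "If only the day is missing for an end date, the last day of the month will be imputed". Then: "If the new estimated date falls after the date of last study visit, the date of last study visit will be used" instead. No further condition is attached.
- **Start date, day missing.** The first of the month is imputed. It is moved to Visit 1 if it falls earlier, but only "while the known month and year match the month and year of the Visit 1 date".
- **Day and month both missing.** "no imputation will be used, and the duration will not be calculated".
- **Complete dates.** No rule alters a complete end date after the last visit.

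SAP Appendix A defines "duration in days = date2 – date1 + 1", for a second date later than the first.

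The protocol does not end AE follow-up at the last visit. Section 8.3.2 states: "All SAEs and nonserious AEs will be followed until resolution, until the condition stabilizes, until the event is otherwise explained", or the subject is lost to follow-up. Subjects permanently taken off drug for a Grade 3 event "should be followed weekly until resolution or stability of the AE" (8.2.1.2.2), and 8.2.1.2.3 says the same for Grade 4. Table 1, footnote v, requires no follow-up visit after early termination.

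Protocol Section 2 lists duration of TEAEs and SAEs with incidence and frequency as an endpoint. SAP 13.2 puts duration in the TEAE listing and summarizes it for AESIs, leaving out AESIs ongoing at end of study.

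**The concern.** The two date rules are meant to do the same job at opposite ends of an event: stop an imputed day from falling outside the study period when the true day is unknown. The start-date rule does this without contradicting the recorded month. The end-date rule does not. Where the recorded end month is later than the month of the last visit, every date compatible with the record lies after that visit, yet the rule assigns the visit date.

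Such records are to be expected, because follow-up runs to resolution or stabilization. Subjects who withdrew because of an AE are among those exposed, since their last visit may come while the event is still open. The error goes only one way, towards shorter events. The same SAP section handles missing causality and severity in the conservative direction.

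**Working it through.** The documents give no figure to reproduce here, so the check applies the rule as written to example dates. The calendar dates are assumptions; the rules are the SAP's.

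**Formulas**

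- SAP end date = the earlier of (last day of recorded month, last study visit).
- Duration = end − start + 1.
- Corrected end date = last visit if the recorded month and year are those of the last visit and month-end is later; otherwise the last day of the recorded month; in no case before onset.

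**Examples, last visit 10 Mar 2022** (an early-termination visit in A and B; no such visit after onset in C and D)

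| Case | Onset | Recorded end | SAP duration | Range the record allows | Corrected |
|---|---|---|---|---|---|
| A | 1 Mar | Apr 2022 | 10 | 32 to 61 | 61 |
| B | 1 Mar | May 2022 | 10 | 62 to 92 | 92 |
| C | 24 Mar | Apr 2022 | −13 | 9 to 38 | 38 |
| D | 20 Mar | Mar 2022 | −9 | 1 to 12 | 1 |

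In A, the SAP takes 30 Apr, resets it to 10 Mar and returns 10 − 1 + 1 = 10 days. The shortest duration compatible with an April end is 1 Mar to 1 Apr, which is 32 days. Had the site recorded 20 Apr in full, nothing would be capped and the duration would be 31 + 20 = 51 days. The result therefore turns on whether a day was entered.

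**Size of the shortfall** (true end − last visit), with the last visit taken over every day of 2022 and the true end day uniform in the recorded month:

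- Recorded month one later than the last visit's: 1 to 61 days, mean 30.4, median 30; at least 7 days in 97.7% and at least 14 days in 90.2% of date combinations.
- Recorded month two later: 29 to 91 days, mean 60.8.

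The 1-day minimum is, for example, a last visit on 31 Mar and resolution on 1 Apr.

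**When the duration is zero or negative.** If the cap applies and onset is k days after the last visit, duration = −k + 1. That is 0 at k = 1 and negative from k = 2 (k = 14 in C, k = 10 in D). An event with onset on or before the last visit always gets at least 1 day.

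**What each part of the repair does.** The month-and-year condition corrects A, B and C. It leaves D at −9, because there the months match; D also needs the rule that the end may not precede the start.

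**The case against.** The literal reading of the rule is hard to dispute. The case against concerns how much follows from it, and much of that case stands.

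- **Narrow trigger.** The record must lack the day, have a known month, and that month must be later than the last visit's. Events under weekly follow-up are the ones most likely to have a full end date. This stands, and the number of records cannot be derived.
- **Negative durations.** A reader might infer that the rule routinely produces them. The documents do not support that. Protocol 8.3.1 collects AEs to the final visit, and 8.1 does not oblige investigators to seek AEs in former subjects. Late onset enters mainly through the looser wording of 6.2.1, which runs to the final visit or contact, or when no early-termination visit is held. Appendix A also defines duration only for a later second date.
- **The duration endpoint as a whole.** A reader might infer that summarized TEAE and SAE durations are biased. The visible SAP plans incidence tables for these; the only visible duration summary is for AESIs. It leaves out events ongoing at end of study, and SAP Section 7 labels Visit 14 as End of Study, so completers' late-resolving AESIs plausibly drop out. For early terminators the SAP does not say what ongoing means.
- **Last study visit is undefined.** If contacts after withdrawal count as visits, the cap moves later and the shortfall shrinks.
- **The listing may still show the recorded end date.** The imputation is stated only for calculating duration. A careful reader could then see the mismatch, but the listed duration would still be wrong.
- **A deliberate on-study window.** SAP 13.2 does restart the clock at Visit 1 for AEs carried over from parent studies. A deliberate window would, however, also cap complete end dates, and it does not.

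**Conclusion.** The rule is wrong as written, with limited reach. For an end date missing only the day, and a recorded month later than that of the last study visit, SAP 13.2 gives a duration the record rules out. The shortfall is at least 1 day. The average of about 30 days rests on the assumption that resolution is uniform over the calendar month after the last visit; the documents give no basis for any particular distribution, so a shortfall of weeks is typical under that assumption and not certain.

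The effect that does not depend on interpretation is on the duration column of the TEAE listings. An effect on the AESI duration summary is possible for early terminators. Incidence, grade, causality and time to onset do not use the imputed end date, and the study is descriptive with no testing, so no main conclusion depends on this point. It is still worth correcting: duration is a named endpoint, the error always makes events look shorter, and the remedy is small.

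**What to change.** In SAP 13.2, make the end-date rule mirror the start-date rule:

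1. Reset the imputed end date to the last study visit only when the known month and year match those of that visit.
2. If the known month is later, keep the last day of the recorded month.
3. Do not let an imputed end date precede the AE start date.

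Item 2 gives the longest duration the record allows (61 days in case A), in line with the month-end convention the SAP already uses.

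It would also help to define last study visit, and to state whether an AESI that resolves after an early terminator's last visit counts as ongoing at end of study.

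The cost is one clause and one programming condition. A few listed durations become longer, and no further data are needed.

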14. A history of or ongoing serious illness or medical, physical, or psychiatric condition(s) that, in the Investigator's opinion, may interfere with the subject's participation in the study, interpretation of results, safety of the subject or ability to understand and give informed consent.
15. Known hypersensitivity to tapinarof or excipients.

Investigational Product, Dosage and Mode of Administration:

Tapinarof cream, 1% is a white to off-white cream containing 1% weight/weight (10 mg/gram) tapinarof, supplied in 30-gram tubes, and is to be administered by the subject or their caregiver OD via topical application of a thin layer to affected areas.

Reference Therapy, Dosage and Mode of Administration:

Not applicable.

Duration of Treatment:

Subjects enrolling in this study may receive treatment for up to 48 weeks. The duration of treatment is based on the vIGA-AD™ score. The end of the study is defined as when the last active subject has completed the Follow-up Visit.

Criteria for Evaluation:

Criteria for Evaluation:	
Efficacy Assessments:	
 • vIGA-AD™ • Eczema Area Severity Index (EASI) • Percentage of total body surface area (%BSA) affected
Functional Outcomes and Quality of Life Assessments:	
 • PP-NRS, for completion by subjects ages \geq 12 years and for completion by caregivers of subjects ages < 12 years • [REDACTED] • [REDACTED] • [REDACTED] • [REDACTED]
Safety Assessments:	
 • AEs • Vital signs • Physical examinations • Clinical laboratory tests • [REDACTED]
Study Endpoints:	
 • Incidence, frequency, and duration of treatment-emergent AEs and SAEs • Change from Baseline in laboratory values • Change from Baseline in vital signs • [REDACTED] • [REDACTED] • [REDACTED] 
 ○ [REDACTED] ○ [REDACTED] ○ [REDACTED] • [REDACTED] 
 ○ Proportion of subjects who achieve vIGA-AD™ = 0 at least 1 time during the study ○ [REDACTED]

- For subjects entering the study with a vIGA-AD™ score ≥ 2 :
 - Proportion of subjects who achieved vIGA-AD™ = 0 or 1 at least 1 time during the study
 - [REDACTED]
- The following endpoints will be summarized over subjects in the intent-to-treat (ITT) population:
 - [REDACTED]
 - [REDACTED]
 - [REDACTED]
 - [REDACTED] change and percent change from Baseline in %BSA affected by visit (OC and LOCF).
 - [REDACTED]

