6.2 Safety Assessments

6.2.1 Adverse Events

All AEs and SAEs will be collected from the time the subject signs the informed consent form (ICF) until the final visit/contact with the subject. AEs that began during the parent study and were ongoing at the end of that study will be reported as ongoing AEs. Additional safety information, including the definition of an AE and the methods for recording, evaluating, and assessing causality of AEs and the procedures for completing and transmitting SAE reports are provided in [Section 8](#).

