For each of these categories, TEAEs will be summarized by SOC in alphabetical order and PT in descending order of frequency. TEAEs ongoing at the end of the previous studies will be considered in the first category (i.e., day of onset ≤ 12 weeks).

At each level of summarization, a subject will be counted once if he/she reported one or more events. The severity of TEAEs and relationship to study drug will be summarized in a similar manner. For summaries of relationship to study drug, a subject will be classified according to related or not related. For summaries of TEAE CTCAE grade, a subject will be classified according to the worst grade.

For treatment-emergent AESIs, summarization will be more extensive, reflecting the more detailed information collected. Information summarized will include number of events per subject, earliest onset day, duration (in days), causality, grade and seriousness of AESIs, outcome, actions taken, assorted physical characteristics of the AESIs, and demographic/baseline characteristics and vIGA-AD™ status of the subjects experiencing them. Each type of AESI will be summarized separately. If a subject has more than one treatment-emergent occurrence of an AESI, the subject's maximum duration, highest levels of causality and seriousness, maximum grade and generally the most extreme level of each characteristic will be summarized. If an AESI was ongoing at end of study (EOS), it will not be included in the duration summary. AESIs ongoing at the end of previous studies will also be included in the summary.

A Kaplan-Meier figure will be generated for each AESI of time to first event for events starting during the study. Time to first onset will be computed as Onset Date of First Occurrence – Date of Visit 1 + 1 if onset date is on or after visit 1 date. Otherwise, time to first onset will be computed as Onset Date of First Occurrence – Date of Visit 1. Subjects not experiencing the AESI will be censored at the date of study completion or discontinuation. AESIs ongoing at the end of the previous studies will not be included.

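### AESI durations carried over from a parent study are cut off at Visit 1 and pooled with full new-onset durations in the AESI summary

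*SAP*

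**What the plan says.** The protocol synopsis lists as a study endpoint "Incidence, frequency, and duration of treatment-emergent AEs and SAEs", and protocol section 2 repeats it. Neither place limits duration to time within this study. Protocol 6.2.1 brings parent-study events into this one: "AEs that began during the parent study and were ongoing at the end of that study will be reported as ongoing AEs".

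SAP 13.2 treats such events as follows.

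- They count as treatment-emergent. The rule for those who rolled over is that "all AEs reported in this study will be considered as TEAEs except for those AEs resolved prior to the Visit 1 date in this study".
- Where events were ongoing at the end of the parent study, "duration will be computed using the DMVT-505-3103 Visit 1 date as the AE start date".
- They enter the AESI summary: "AESIs ongoing at the end of previous studies will also be included in the summary".
- A subject with several occurrences of an AESI contributes "the subject's maximum duration, highest levels of causality and seriousness, maximum grade".
- A separate rule removes unresolved events: "If an AESI was ongoing at end of study (EOS), it will not be included in the duration summary".

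The incidence rows in SAP 13.2 are given with and without events ongoing from the previous studies. No such split is stated for duration. The Kaplan-Meier figure of time to first AESI leaves carried-over events out.

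**The concern.** The Visit 1 rule sits under the heading on imputing dates, but it is not a missing-data rule, because it applies when the onset date is fully known. Protocol 8.1.3 asks sites to collect duration and time to onset for each AESI. The TEAE listing carries an onset date beside the parent-study flag and the duration. The SAP already takes baseline values from the parent studies (SAP 10.2). The true onset therefore appears recoverable.

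The result is a summary line that mixes two quantities: full duration for new events and time since rollover for carried-over ones. The error runs in one direction and touches only some columns. Tapinarof (Pivotal), Vehicle (Pivotal), Total (Pivotal), Tapinarof (2104) and Total (Overall) can all contain carried-over events; Direct-Enroll cannot. At stake is how persistent contact dermatitis, follicular events and headache appear in a long-term safety study.

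**Working it through.** The documents state no duration figure, so there is nothing of the plan's own to reproduce.

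**Inputs.** SAP Appendix A defines duration as end date minus start date plus 1. Visit 1 falls at completion of the pivotal Week 8 visit or the 2104 Day 28 visit (protocol Table 1, footnotes a and b). I take pivotal Week 8 as parent Day 57, the numbering this study uses for its own Week 8; the parent protocols are not available. The follow-up visit is Day 344 (protocol 7.5).

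**Loss per event.** With onset on parent day *s*, Visit 1 on parent day *v* and resolution on extension day *r*:

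- reported duration = *r*
- duration from true onset = (*v* + *r* − 1) − *s* + 1 = *r* + (*v* − *s*)
- loss = *v* − *s*, at most 57 − 1 = 56 days (pivotal) or 28 − 1 = 27 days (2104) for onset on or after parent Day 1

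| Parent onset | Resolved, extension day | Reported | From true onset |
|---|---|---|---|
| Pivotal Day 14 | 10 | 10 | 53 |
| Pivotal Day 1 | 5 | 5 | 61 |
| Pivotal Day 1 | 100 | 100 | 156 |
| Pivotal Day 1 | 344 | 344 | 400 |
| 2104 Day 1 | 5 | 5 | 32 |

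**Maximum rule.** If the subject in the first row later has a new 12-day event of the same type, the table shows max(10, 12) = 12. From true onset it would show max(53, 12) = 53.

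**Typical loss.** Only events that survive to rollover are carried over, which favours late onsets. With uniform onset over *L* = 56 days and exponential durations of mean *m*, the mean loss is *m* − *L*·e^(−*L*/*m*)/(1 − e^(−*L*/*m*)). For *m* = 30 this is 30 − 56 × 0.1546/0.8454 = 19.8 days. For *m* = 14 it is about 13 days.

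**Effect on the pooled mean.** This was simulated with 1,000,000 events per scenario. The assumptions are mine, not the documents': onset uniform over 56 parent days plus 343 extension days, one event per subject, and events ongoing at end of study excluded. The three middle scenarios, with means in days:

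| Assumed duration | Carried-over share | New-onset | Carried-over, reported | Carried-over, true | Pooled, reported | Pooled, true |
|---|---|---|---|---|---|---|
| Exponential, mean 30 | 7.5% | 27.2 | 30.0 | 49.7 | 27.4 | 28.9 |
| Lognormal, median 30, sigma 1 | 9.9% | 38.0 | 46.3 | 67.8 | 38.9 | 41.0 |
| Gamma, shape 4, mean 30 | 8.6% | 29.3 | 19.0 | 36.6 | 28.4 | 29.9 |

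In these three the pooled mean falls by 1.5/28.9 = 5.2%, 2.1/41.0 = 5.1% and 1.5/29.9 = 5.0%. Over all ten scenarios run (exponential means 14 to 120, lognormal medians 14 to 60, gamma means 14 to 60) the fall ranges from 0.4/14.0 = 2.9% to 3.5/58.1 = 6.0%, and carried-over events make up 4.0% to 15.5% of those summarised.

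**The case against.** The best defence is that time within the study is a coherent quantity. The SAP counts study days from Visit 1, and it puts carried-over events in the first onset window. In Direct-Enroll, too, every counted day falls in the extension. For vehicle rollovers, the time before Visit 1 was on vehicle, so adding it to a total labelled as tapinarof would mislead in its own way. The rule is stated openly, the listing flags carried-over events, the study is descriptive, and no decision depends on AESI duration.

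Much of this stands. It supports keeping the Visit 1 duration as one labelled result. It does not support showing that quantity unlabelled and pooled with full durations, under an endpoint that does not say within-study.

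A reader might also infer that the longest-running AESIs come out as short ones. The documents do not support that. The loss is capped by the length of the parent study, and a carried-over event can still be reported at about 344 days. In the simulation, carried-over events are reported as shorter than new ones only when durations are nearly fixed (gamma); under the exponential and lognormal assumptions they are not. The longest events are mostly those still ongoing at end of study (true mean 60.2 days in the exponential mean-30 case), and a different rule drops them altogether.

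Nor is the mean loss simply half the parent study, 28 days for the pivotal studies. That would require essentially every event to last until rollover, whatever its onset day.

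**Conclusion.** The point holds as a bias of known direction and limited size. Every carried-over AESI is understated by its parent-study run time, and the shortened values are pooled with full ones in the rollover and total columns. Individual values can be badly wrong (53 days shown as 10), and the greater persistence of carried-over events largely disappears: 49.7 true days against 30.0 reported in the exponential mean-30 case.

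The shift in the pooled mean is probably only about 3-6%. That range rests on the assumed distributions, a constant event rate and one event per subject. It describes pivotal rollovers only and leaves the maximum rule out. If AESIs cluster early in treatment, the share carried over by tapinarof rollovers, and so the effect in that column, would be larger. The 56-day and 27-day caps assume onset on or after parent Day 1. This is a cheap improvement to a descriptive summary; no conclusion of the study turns on it.

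**What to change.** In SAP 13.2:

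1. Summarise AESI duration on separate lines for new-onset and carried-over events, as the incidence rows already do.
2. For carried-over events, report duration twice: from the onset date recorded in the parent study, and from Visit 1, the latter labelled *duration within DMVT-505-3103*.
3. Do not pool full-length carried-over durations with new-onset ones. Events ongoing on a fixed date are a length-biased sample (49.7 against 27.2 days in the exponential mean-30 case), so the pooled figure would then be too long for sampling reasons alone. For vehicle rollovers it would also add days on vehicle.

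The cost is SAP wording, a merge of parent-study onset dates, extra table lines and longer reported durations for carried-over events. No new data collection appears to be needed.
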